#### **7.7.4 Year three interim feasibility assessment**

At the end of the third year from Registry initiation, feasibility will be re-assessed by the Sponsor. In particular, projections will be made to estimate the number of live births expected 10 years after launch (i.e. at target end date of study). This estimation will be done in an integrated manner taking into account all data sources as described in [Section 7.5.2](#).

As reference, if the projected number of live births after 10 years in the siponimod exposed cohort is less than 100, consideration will be made regarding study discontinuation. Note that these reference thresholds are indicative only and the final decision will be taken based on the totality of evidence accumulated until that point in time.

#### **7.7.5 External comparisons**

The overall rate/proportion of major structural defects will be compared with the most recently available rate/proportion published from the MACDP to place the internal comparison group rates in context. However, it should be noted that the MACDP rates for major birth defects represent a population from one urban city that differs in many respects from the sample of women with the indications that are eligible for this study, and the methods of ascertainment do not allow for identification of major structural defects that do not result in hospitalization.

#### **7.7.6 Evaluation for a pattern of major and minor structural defects**

The following steps will be taken to evaluate any pattern of major structural defects as described in [Chambers et al 2001](#):

- A review of major structural defects will be made by category. A review of specific major structural defects will be conducted taking into consideration timing, dose, and biological plausibility.
- Major structural defects identified in aborted fetuses will be reviewed separately from the primary analysis for the live born infants.

- Among infants with three or more minor structural defects, the siponimod-exposed group will be examined for evidence of a specific pattern of 3 or more minor structural defects in any 2 or more children. If such a pattern is identified, Comparison Groups 1 and 2 will be evaluated for any evidence of the same pattern. ([Chambers et al, 2001](#))

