## 6 Research question and objectives

The purpose of the Siponimod Pregnancy Exposure Registry is to evaluate the effect of siponimod exposure on rates of pregnancy and infant outcomes in exposed pregnancies compared to unexposed disease-matched and healthy unexposed pregnancies. The lack of human fetal safety data for siponimod makes such a monitoring system an important component of epidemiologic research on the safety of this drug.

The primary objective is to estimate and compare the prevalence of major structural defects in siponimod exposed pregnant women versus 1) disease-matched pregnant women not exposed to siponimod, and 2) healthy pregnant women.

The primary objective will be evaluated among i) pregnancies ending in at least one live birth, and ii) pregnancies ending in at least one live birth, spontaneous abortion, still birth or termination of pregnancy

Secondary objectives are to estimate and compare the prevalence of selected adverse pregnancy and infant outcomes in siponimod-exposed pregnant women versus 1) disease-matched pregnant women not exposed to siponimod, and 2) healthy pregnant women.

Mayzent exposure is defined as exposure to siponimod any time from the 4th days post the first day of LMP prior to conception up to and including the end of pregnancy.

- The primary outcome of the study is major structural defects.
- The secondary outcomes of the study are:
  - Spontaneous abortion/miscarriage
  - Stillbirth
  - Elective termination
  - Preterm delivery
  - Preeclampsia / eclampsia
  - Pattern of 3 or more minor structural defects
  - Small for gestational age
  - Postnatal growth small for age at approximately one year of age
  - Developmental performance at approximately one year of age
  - Serious or opportunistic infections in the first year of life.

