### 7.5.1 Determination of sample size

The sample size for this study is not only based on the statistical considerations to address the question of interest but also takes into account the feasibility aspects, prior experience and available literature ([Krueger et al 2017](#)) on conduct of pregnancy registries in the MS disease area.

In the three cohorts, approximately 867 pregnant women will be enrolled in US and Canada with a ratio of 1:1:1.

Based on previous experience with MotherToBaby/OTIS Pregnancy Studies, it is estimated that subjects will be an average of 7-10 weeks post-LMP at the time of enrollment. Given this mean gestational timing at enrollment, the anticipated spontaneous abortion/stillbirth rate is 10%, the estimated elective abortion rate is 5%, and the estimated lost to follow-up rate is 5% ([Chambers et al, 2016](#)). This will result in known outcomes for approximately 273 pregnancies in each cohort, including 231 pregnancies with at least one live born infant in each cohort at the end of recruitment.

Baseline rates of major structural birth defects, specific patterns of three or more minor structural defects, premature delivery, and small for gestational age are based on previous MotherToBaby/ OTIS studies and on general population data. Rates of spontaneous abortion in the general population are 15-20% ([Avalos AL, et al 2012](#), and [Magnus et al 2019](#)). However, since women do not typically enroll in pregnancy registries until after 7-8 weeks' gestation when the highest risk of spontaneous abortion has passed, the baseline estimate is drawn from previous OTIS studies. [Table 7-4](#) gives the minimum detectable effect sizes with 80% power (two-sided significance level 0.05, except as noted below for pattern of minor structural defects), for the comparisons described above. If the disease-matched comparison and the healthy comparison groups are comparable, then consideration will be given to pooling data in the two comparisons cohorts for analysis, as shown in [Table 7-5](#). The current sample size provides 80% power to detect a risk ratio of approximately 4.4 or greater in major structural defects compared to the baseline prevalence of 3% in the comparison groups. This is consistent with the population prevalence of major structural defects of 2.8% in the Atlanta metropolitan area ([CDC 2017](#)).

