**Table 7-4 Sample Size and Detectable Effect Size with 80% Power for Comparison of Exposed Cohort 1 to Unexposed Cohort 2**

Endpoint	N per group	Rate in comparison group	Relative risk	Power
Major structural defects b	231	3%	3.0	80%
Specific pattern of 3 or more minor structural defects	231	1%	4.6	80% c
Spontaneous abortion/still birth	259	10%	1.9	80%

Endpoint	N per group	Rate in comparison group	Relative risk	Power
Preterm delivery	231	10%	1.9	80%
Small for gestational age	231	10%	1.9	80%

aAll tests are two-sided with alpha = 0.05, based on Fisher's exact test, unless specified otherwise. Calculations conducted using R.

bPrimary endpoint; among livebirths.

cOne-sided

**Table 7-5 Sample Size and Detectable Effect Size with 80% Power for Comparison of Exposed Cohort 1 to Unexposed Cohorts 2 and 3 Combined**

Endpoint	N in exposed group	N in comparison group	Rate in comparison group	Relative risk	Power
Major structural defects b	231	462	3%	2.7	80%
Specific pattern of 3 or more minor structural defects	231	462	1%	4.0	80% c
Spontaneous abortion/still birth	259	518	10%	1.7	80%
Preterm delivery	231	462	10%	1.8	80%
Small for gestational age	231	462	10%	1.8	80%

aAll tests are two-sided with alpha = 0.05, based on Fisher's exact test, unless specified otherwise. Calculations conducted using R.

bPrimary endpoint; among livebirths.

cOne-sided

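### The minor-defect pattern is chosen from the exposed infants and only then sought in the comparators, which biases the comparison toward an exposed excess

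*Protocol*

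**What the plan says.** Protocol section 7.7.6 sets a fixed order. The search is confined to infants with three or more minor defects, where "the siponimod-exposed group will be examined for evidence of a specific pattern of 3 or more minor structural defects"; a pattern counts once at least two exposed children share it. The comparators enter only at the next step, and only on condition: "If such a pattern is identified, Comparison Groups 1 and 2 will be evaluated for any evidence of the same pattern". No search starts from the comparison groups.

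The same outcome is also treated as an ordinary between-group endpoint. Section 6 lists "Pattern of 3 or more minor structural defects" among the secondary outcomes, under an objective to estimate and compare prevalence between the exposed cohort and each comparator. Table 7-4 has a row for "Specific pattern of 3 or more minor structural defects": 231 per group, 1% in the comparison group, relative risk 4.6, 80% power, one-sided. Table 7-5 gives relative risk 4.0 for 231 against 462 pooled comparators.

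Section 7.4.3.5 blinds the infant examinations to cohort. Section 7.7.7 provides for independent evaluation of photographs, and re-examination if needed, once a pattern is identified. Section 7.7.3.1.2 separately plans a GEE analysis of minor structural defects.

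**The concern.** The exposed infants both generate the hypothesis and supply the count compared. Once a pattern is declared, the exposed count has been truncated to two or more, while the comparator count is an unselected draw. Chance clusters in comparator infants are not looked for, so the registry does not produce the background frequency of such clusters that a reader would need in order to judge an exposed one.

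A detectable relative risk with a fixed comparator rate presupposes a pattern defined without reference to the data, so Tables 7-4 and 7-5 do not fit the procedure in section 7.7.6. Section 5 describes siponimod as teratogenic in rats. In that setting, a chance cluster in two exposed children that is not seen in comparators could easily be read as a drug-related embryopathy.

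**Working it through.** **Inputs from the protocol.** n = 231 per group, from section 7.5.1 ("including 231 pregnancies with at least one live born infant in each cohort at the end of recruitment"); pattern rate in the comparison group q = 1% (Table 7-4); declaration rule of at least two exposed children (section 7.7.6). Section 7.5.1 sets the level as "two-sided significance level 0.05, except as noted below for pattern of minor structural defects", and the table notes mark the pattern rows as one-sided.

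**Assumptions.** One infant per pregnancy, all examined, and the same true rate q in every cohort (no effect). Rates other than 1% are assumed, because the protocol gives none.

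**The plan's own figure.** Arcsine power, one-sided 0.05, with h = 2·asin√p1 − 2·asin√p2 and power = Φ(h·√(n1·n2/(n1+n2)) − 1.645):
- Table 7-4, 4.6% against 1%: h = 0.4323 − 0.2003 = 0.2320; h·√115.5 = 2.493; power = Φ(0.848) = 80.2%.
- Table 7-5, 4.0% against 1%: h = 0.4027 − 0.2003 = 0.2024; h·√154 = 2.511; power = Φ(0.867) = 80.7%.

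Both match the stated 80%. The test named in the footnote ("based on Fisher's exact test, unless specified otherwise. Calculations conducted using R") gives 69.1% and 74.0% when computed exactly and one-sided, so the tables match an approximation and not Fisher's test. Either way, the calculation treats the pattern as given in advance.

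**Effect of the selection, one pattern, no drug effect.** Let X be the exposed count, binomial(231, q). A pattern is declared only if X ≥ 2, so E[X | X ≥ 2] = (231q − P(X=1)) / (1 − P(X=0) − P(X=1)). The count in one comparison group has the unselected mean 231q.

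At q = 1%: P(X=0) = 0.0981, P(X=1) = 0.2289, P(X≥2) = 0.6730. Expected exposed count = (2.310 − 0.2289)/0.6730 = 3.09, against 2.31 in the comparator; ratio 1.34.

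| Pattern rate q | P(declared) | Exposed mean, if declared | Comparator mean | Ratio | Exposed higher / tied / lower |
|---|---|---|---|---|---|
| 0.1% (assumed) | 2.3% | 2.08 | 0.23 | 9.0 | 97.9 / 2.0 / 0.2% |
| 0.2% (assumed) | 7.9% | 2.16 | 0.46 | 4.7 | 93.1 / 5.9 / 1.0% |
| 0.5% (assumed) | 32.1% | 2.46 | 1.16 | 2.13 | 75.9 / 16.0 / 8.0% |
| 1% (protocol) | 67.3% | 3.09 | 2.31 | 1.34 | 56.7 / 19.3 / 24.0% |
| 2% (assumed) | 94.6% | 4.84 | 4.62 | 1.05 | 45.7 / 14.0 / 40.3% |

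Without selection, the exposed count at 1% would be the higher one in 40.4% of studies, and by symmetry the lower one equally often.

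**Search over many possible patterns.** Three groups of 231 infants were simulated with 130 checklist items (the approximate number in section 7.4.3.5) and no effect, at assumed mean item prevalences of 0.5% to 3%. A pattern was taken as three items shared by at least two exposed infants, and the most frequent one was followed. Such a pattern appeared in 0.1% to 99.4% of studies, depending on the assumed prevalence. When one appeared, the exposed count exceeded that of Comparison Group 1 in 98.6% to 100% of studies. A one-sided Fisher test at 0.05 then rejected in 0% to 0.3% against Group 1, and in 0% to 21.6% against pooled comparators.

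**Pooled, masked search, same null.** The lean disappears. The exposed count was higher in 33.7% and lower in 35.6% (items at 2%); 38.6% and 36.8% (skewed, mean 2%); 31.7% and 37.1% (skewed, mean 1%).

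**The case against.** The best defence is that section 7.7.6 is signal detection. It names no estimator and no test, and the comparator check can refute a signal as well as support one. The infant examinations are blinded, an identified pattern triggers independent photograph evaluation, and a separate GEE analysis of minor defects does not depend on an exposed-derived pattern.

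Much of this stands, and it limits the point. It does not remove it. Blinding and photograph review govern how individual defects are recorded, not how the pattern is selected. The GEE analysis is unaffected but does not correct the pattern comparison. The descriptive reading also conflicts with the protocol's own choice to list the pattern as a compared secondary outcome and to power it.

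A reader might infer three stronger things that the documents do not support:
- **That an exposed excess is guaranteed.** The rule guarantees two exposed carriers once a pattern is declared, and no more. Often no pattern will be declared, and at 1% one comparison group ties or exceeds the exposed count in 19.3% + 24.0% = 43.3% of declared cases.
- **That a false significant result is likely.** Against Group 1, the primary comparator, rejections were at most 0.3%. The 21.6% needs one skewed-prevalence assumption and pooled comparators, and section 7.5.1 makes pooling conditional on comparability.
- **That the search breaks the examination blinding.** Selecting the pattern as written requires cohort labels, but it works on findings already recorded blind.

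Nor should the null ratios at 0.1% or 0.2% be set against the 4.6 in Table 7-4, which refers to one pattern at 1%.

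**Conclusion.** The point holds as a directional bias. Taking the pattern from exposed infants and then looking for it in comparators tilts the comparison toward an exposed excess when siponimod has no effect, and the powered rows in Tables 7-4 and 7-5 do not describe that procedure. At the protocol's 1% rate the tilt is moderate: ratio 1.34, exposed higher in 57% and lower in 24% of declared cases. It grows as the pattern gets rarer, to about 4.7 at 0.2% and 9.0 at 0.1%, and it nearly vanishes at 2% (1.05). The direction follows from the rule alone. The size away from 1% and the many-pattern results rest on assumed rates. One secondary outcome is affected; the major-defect analysis and the GEE analysis of minor defects are not. The change is worth making because it is cheap and removes the bias.

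**What to change.** In section 7.7.6, have the dysmorphologists search a pooled, cohort-masked list of all infants with three or more minor defects for patterns shared by two or more children. Lock the list of patterns, then unmask and tabulate each pattern by cohort. Any pattern shared by two exposed infants is still found.

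If the exposed-first search is kept, label it descriptive signal detection, state that its counts are selected, and remove the pattern rows from Tables 7-4 and 7-5.

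The masked search needs no new examinations, because the same checklist is used in all three cohorts. It costs some extra review time, since comparator infants are included from the start. Photographs will be available only where parents consented.

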#### **7.7.7 Inter-rater reliability**

There may be variability in the assessment of minor structural defects among the study dysmorphologists. This will be addressed in three ways:

- The participating dysmorphologists have been working with this study protocol in the existing OTIS Autoimmune Diseases in Pregnancy Project for 10 or more years, and have participated in group training and evaluation exercises. These reliability evaluations involve having examiners independently examine the same infant and comparisons of exam results and measurements are made. These evaluation exercises will continue periodically throughout the duration of this Registry.
- If a pattern of minor structural defects is identified in the interim or final analysis of the study data, photographs of the infants exhibiting this pattern will be independently evaluated by other examiners, and if deemed necessary, affected children can be reexamined by 1 of the other dysmorphologists to ensure agreement.
- In previous studies involving the evaluation of minor structural defects, certain minor structural defects tended to be less reliably detected than others. This raises the possibility of missed identification of a pattern that includes 1 or more of those defects. If the interim reports or final analysis suggest that one or two minor structural defects occur substantially more frequently among exposed infants regardless of examiner, and among these children an additional defect or defects has been identified only by certain examiners, it may be necessary to have infants with those defects re-examined by one of the other dysmorphologists.

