#### **7.4.3.5 Dysmorphology evaluation**

All live born infants will be eligible for an exam by one of a team of study-dedicated dysmorphologists, led by the study Co-investigator, from the [REDACTED]. The team is made up of licensed pediatricians with subspecialty fellowship training in dysmorphology/genetics. The physical examinations evaluate infants for both major and minor structural defects and provide increased sensitivity for detecting a specific pattern of malformation should one exist. Infants will be examined within the first year of life or as soon as the examination can be practically arranged. The Research Center will group and schedule these follow-up examinations to meet the study criteria of infant age, to maximize physician blinding as to exposure status, and to minimize travel time and expense. The examiner travels to the patient to conduct the examination.

Infant examinations will be conducted using a standard checklist of approximately 130 minor malformations included in a standard physical evaluation form. In addition, with parental consent, digital photographs of the infant will be taken to aid in validating any findings across examiners.

Dysmorphologists will perform these examinations blinded to the exposure or comparison group status of the mothers. Because subjects may have visible evidence of their disease, the use of a disease-matched comparison group allows for preservation of physician blinding. Mothers are asked to sign a consent for medical photographs at the time of the examination. If deemed necessary, the examiners will meet to review photographs of children to assess any patterns that may be identified.

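### Section 7.7.7 lets an exposed-only excess in a few of about 130 minor-defect items start a second examination, without a threshold, a mirror rule for comparators, or stated blinding

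*Protocol*

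**What the plan says.** Section 7.4.3.5 has each live-born infant examined against a "standard checklist of approximately 130 minor malformations", and states that "Dysmorphologists will perform these examinations blinded to the exposure or comparison group status of the mothers". Photographs are taken with parental consent to help validate findings across examiners.

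Section 7.7.7 lists three ways of handling examiner variability. The third concerns items that are detected less reliably, which could cause a pattern to be missed. It applies when two conditions hold together:

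- The results, at an annual report or at the end of the study, "suggest that one or two minor structural defects occur substantially more frequently among exposed infants regardless of examiner".
- Some of those infants also have one or more further defects that only certain examiners recorded.

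The consequence is optional: "it may be necessary to have infants with those defects re-examined by one of the other dysmorphologists".

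A pattern of three or more minor defects is a listed secondary outcome (section 6). Section 7.7.3.1.2 compares minor defects by GEE. Section 7.7.6 looks for a specific shared pattern in two or more exposed children first, and in the comparison groups only if one is found. Section 7.7.9 makes the interim reports descriptive, without statistical comparisons.

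**The concern.** The trigger looks in one direction over many items. Nothing fixes how large an excess counts as substantial, how many cases it needs, which comparison group it is measured against, or how the number of items is allowed for. In the interim reports no test is available, so the judgement is made by eye.

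The consequence is also one-sided. Items are chosen because exposed infants show more of them, so carriers of those items are mostly exposed. The step exists to find what a first examiner may have missed, so it adds defects more readily than it removes them. There is no matching step when comparators show the excess. If the added findings enter the compared counts, exposed infants have been searched harder than comparators for a listed secondary outcome. A genuine signal would also be open to the criticism that selective re-examination had produced it.

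**Working it through.** **Inputs from the protocol.** About 130 items (7.4.3.5); cohorts "with a ratio of 1:1:1", "including 231 pregnancies with at least one live born infant in each cohort" (7.5.1); comparison rate 1%, relative risk 4.6, 80% power, one-sided, for "Specific pattern of 3 or more minor structural defects" (Table 7-4).

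**Assumptions.** Item prevalences are not given and are assumed. Items are independent, there is no drug effect, one infant per pregnancy and one look at the data.

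**1. The plan's own figure.** The arcsine formula gives power = Φ(h·√(n/2) − 1.645), with h = 2·asin√0.046 − 2·asin√0.01 = 0.232 and n = 231. That is Φ(0.232 × 10.75 − 1.645) = Φ(0.85) = 80.2%, so the 4.6 is reproduced. (One-sided Fisher, the test named in the table footnote, gives 69.0%. That is a separate matter and does not bear on this point.) A 1% rate is 0.01 × 231 = 2.3 infants per cohort.

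**2. Chance of meeting the first condition.** For one item, with X and Y independent Binomial(231, p), let q be the probability of qualifying. Over 130 items the chance of at least one is 1 − (1 − q)^130.

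| Reading of 'substantially' | q at p = 1% | At least one item, p = 0.5% / 1% / 2% | Mixed prevalences, 0.1% up to 1% / 2% / 4% |
|---|---|---|---|
| Ratio ≥2, ≥5 exposed cases | 0.0562 | 53% / 99.9% / 100% | 64% / 99% / 99.7% |
| Ratio ≥3, ≥5 exposed cases | 0.0355 | 45% / 99% / 100% | 53% / 89% / 95% |
| One-sided Fisher p ≤0.025 | 0.0035 | 5% / 37% / 72% | 5% / 19% / 36-40% |

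The mixed column spreads items log-uniformly and is the more realistic one. The 72% arises only if every item has 2% prevalence. With 100 infants per cohort (the live-birth reference figure in 7.7.4), the doubling rule is met in 4.5% / 37% / 94% of studies with mixed prevalences.

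**3. Adding the second condition.** With four examiners assumed, the doubling rule plus the examiner condition is met in 61% / 99% / 99.7%, against 64% / 99% / 99.7% without it. It filters little, because affected infants nearly always carry some other item that not every examiner recorded.

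**4. Who is re-examined.** Simulation: 231 against 231 infants, true prevalence 1% per item, each examination detecting 60% or 80% of true defects, and re-examination of carriers of the two items with the largest exposed excess. On average about 9 (60%) to 11 (80%) exposed infants carry them, against about 1 comparator.

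**5. Effect if both examinations are combined for the exposed carriers.**

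- Among the re-examined infants, the number with three or more defects rises from about 1.6 to 2.6 (60%) or 2.8 to 3.6 (80%).
- In the whole exposed cohort it rises from 10.1 to 11.1 (60%), or 1.0/10.1 = 10%, and from 20.1 to 20.9 (80%), or 0.8/20.1 = 4%. Without re-examination the comparators stand at about 10 and 20.
- Over prevalences of 0.5%, 1%, 2% and a 0.1-4% mix, the rise is about 2% to 16%.
- Re-examination newly creates two exposed infants sharing the same three defects in about 0-3% of null runs. The least favourable setting (2% prevalence, 80% detection) gave 4% in 3,000 runs.

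**The case against.** Several stronger readings are tempting, and the protocol does not support them.

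- **That a false trigger happens in most null studies.** This depends on how 'substantially' is read and on prevalences the protocol does not give. Under a nominal-significance reading, or with small cohorts and rare items, it is not so. Expert board review of the annual data also means that no mechanical ratio cut-off is applied.
- **That an exposed excess alone is enough.** Section 7.7.7 also requires the examiner-dependent further defect, and makes re-examination optional. The second condition filters little, but it is part of the rule.
- **That the second examination is unblinded.** Section 7.7.7 is silent. Section 7.4.3.5 states blinding for the study examinations, and nothing lifts it. What can be said is that calling back mainly exposed infants tends to reveal their status.
- **That re-examination findings are added to the counts.** No text says so. Section 7.7.2.4 identifies minor defects only through the study examination and does not say whether a second one counts. The aim of not missing a pattern suggests it might, and the SAP could settle it.
- **That a false teratogenic pattern is likely.** Section 7.7.6 needs a specific shared pattern, not any three defects, and seeks it in both comparison groups. Section 7.7.7 also has other examiners review photographs of infants who show it. The simulated risk is small.

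What remains is the asymmetry. Re-examination is a data-collection step fixed in the protocol, it is prompted only by an exposed excess, and it has no counterpart in comparators.

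**Conclusion.** The concern holds in a limited form. The re-examination rule has no threshold or multiplicity allowance, can readily be met by chance, has no mirror rule for comparators and does not state blinding. If its findings enter the compared counts, ascertainment of minor defects is differential.

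The likely bias is modest: around one extra exposed infant with three or more defects at 1% prevalence, and rarely a false shared pattern. That extra infant is still not negligible beside the 2.3 per cohort implied by the planning rate for a specific pattern, although not every such infant would show one specific pattern. These sizes rest on assumed prevalences, detection rates, independent items and the combining of both examinations for exposed carriers. Only one secondary outcome is affected; the primary outcome is not. The change is worth making because it costs little.

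**What to change.** In section 7.7.7, state that the compared minor-defect and pattern counts (sections 7.7.3.1.2 and 7.7.6) use the first, blinded examination only, and that re-examination findings are reported separately and descriptively. The exploratory pattern review stays available.

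Where the reliability of an item is in doubt, have one of the existing dysmorphologists, blinded to cohort, read the photographs already taken, in a set with an equal number of comparator infants. Merely extending re-examination to carriers in all cohorts would not restore balance, because the items were picked for an exposed excess.

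The cost is a wording change and some reading time. The downside is small: defects found only at re-examination do not enter the formal comparison, and photographs exist only where parents consented.
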